12.2 Sample Size Determination

Statistical power and sample size: All sample size estimates here assume a minimum of 80% power and a two-sided alpha of 0.05. We employ the method for the computation of sample size for cross-sectional stepped wedge studies comparing intervention to usual care in two-group statistical analyses. This method incorporates information on the number of steps used in the

stepped wedge/cluster randomized design, the number of subjects per time period, and the degree of clustering via the intraclass correlation coefficient (ICC) to compute the design effect, the factor by which the sample size found to provide sufficient statistical power for a meaningful intervention difference in outcome assuming independent data is multiplied. For the primary outcome of the documentation of ACP in the medical record, a sample size of 440 records per group in a chi-squared test for independent data will provide 80% power at a two-sided alpha of 0.05 to detect a difference in the proportion of subjects with notation of 35% in the intervention group compared to 25% in the usual care group, values consistent with prior research and expectation based on clinical data from the two health systems estimated from recent data. Based on our planned number of steps (7 with one uniformly applied usual care period across all hospital units), enrollment per study period, and a reasonable ICC of 0.01, the design effect is 2.72. Thus, we will need to obtain outcome data from the records of at least 2394 subjects overall (1197 per health system) to provide 80% power for our analysis of intervention effectiveness. We anticipate, however, that as many as 15,000 records will be available for analysis with respect to the documentation of ACP. Thus, our planned sample size for our primary records-based analysis on 15,000 records will therefore provide more than adequate power to test for differences in our primary outcome.

Data for Aim 1 is derived from the EHR and as is typical for trials that integrate new initiatives within the workflow of large institutions in a SW-CRT that does not involve consent. Indeed, we have been previously approved by multiple IRBs for such activities. Along with our exceedingly efficient NLP-assisted and human-confirmed software method for EHR data extraction, we can have a very large study sample with for this activity.

Please note: We anticipate the population under study in Aim 1 to exceed that required by a simple application of the power calculation presented above. However, this is warranted for eight reasons. First, the size of this observed population gives us the opportunity to examine intervention effects for less common outcomes. Second, this sample size will allow us to evaluate potential heterogeneity in treatment effects for subpopulations as small as 20% of the population. Third, this sample size provides an experimental context in which we will be able to recruit a population of 600 patients with ADRD/Delirium and their associate caregivers for surveying. Indeed, to sustain the activities of Aim 2, we need a large population to draw from, as many of the people under study for Aim 1 would not be eligible for participation in Aim 2. Fourth, the size of the population for Aim 1 also protects this trial from the potential that we will have significantly varying sizes of study clusters, a factor that is often neglected in sample size assessments for SW-CRTs.(145) Indeed, this is a likely phenomenon as hospital units vary significantly in their population of patients. Fifth, there is minimal risk to human subjects presented by the expanded sample size for Aim 1. Indeed, this educational intervention is being spread across the clinical units of our two hospitals in a pragmatic manner as part of the standard of care. The research activities of Aim 1 involve no direct burden to patients as there is no consent process and data for this activity will be derived from the EHR. The chief risk is the loss of confidentiality and robust protections are in place to protect patients from this potential risk. Sixth, we plan to extend this intervention as a new clinical initiative in our two health systems in a manner (time per cluster) that has been endorsed by leadership as a reasonable rate for dissemination (i.e., we are not adding more time). Seventh, we have devised an exceedingly efficient and accurate method for outcome assessment (i.e., we are not adding more

cost). Eighth, we will protect against inappropriate conclusions. We understand that treatment effect sizes will be more relevant than p-values and that clinical significance is the goal (not simply statistical significance).(146, 147) We have set an absolute increase of 10%, i.e., an increase of ACP documentation during the index hospitalization from 25% to 35%, as the benchmark for clinical significance. **In summary, the size of Aim 1 is needed to be able to do Aim 2b and we have taken appropriate measures to ensure that the research design for Aim 1 does not yield consequences for being overpowered.**

For the interview survey derived outcomes (knowledge, confidence in future care, communication satisfaction, decisional satisfaction, and decisional conflict) with approximately 600 subjects available across the 7 “clusters”/steps, the resulting design effect is 2.03 (again, assuming an ICC of 0.01). For this analysis sample size, the minimum effect size that can be detected for the uncertainty and knowledge scores separately with 90% power and alpha=0.05 would be 0.53 after applying the design effect. ***In sum, our anticipated sample sizes for both our primary and secondary aims will provide adequate statistical power to detect moderately sized and clinically important effects of the intervention and account for the cluster-randomized nature of our stepped wedge study design.***

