For Aim 2b, 600 caregivers of patients with ADRD/Delirium (300 control phase; 300 intervention phase) will be surveyed by telephone during (or within one week of) the index hospitalization to assess caregiver-centered outcomes.

Each day PCEs, who will be nurses or social workers on the palliative care team, will approach patients who are currently hospitalized under Aim 1 or Aim 2a. The PCE will then proactively use the goals-of-care video decision aid (or any of the additional videos regarding CPR, hospice, dementia, etc., as relevant and in the appropriate language) to provide educational support and assist in delivering primary palliative care services relating to goals-of-care conversations and ACP documentation. The videos range from 4-6 minutes in length and the PCE will watch the videos together with the patient and caregiver on an iPad (or remotely via telehealth with the caregiver).(130)

The PCE will arrange all video showings to include patient and caregiver (when possible and acceptable to the patient); when patients are unable to view a video (e.g., loss of capacity, delirium), the caregiver will view the video. The videos do not replace clinician counseling; indeed, they are designed to allow the PCE to confirm comprehension and to stimulate

conversation with a shared vocabulary. The PCE will then communicate the patient's or caregiver's wishes to the treating primary medical team to coordinate care.

In cases when the PCE deems that engagement with the full palliative care team is warranted, they will approach the treating primary medical team to place the consult. If/when the PCE exhausts the automated list for patients, they will coordinate with the palliative care consult team to select patients from the list of requested consultations. The PCE role will be fully integrated into existing hospital practices at our sites consistent with the pragmatic nature of this study design.

For Aim 1, the study population will consist of patients 65 years or older who are admitted to one of the study inpatient units in the hospital. For Aim 2a, the study population will consist of any patient ≥ 18 years admitted to one of the study inpatient units in the hospital with a diagnosis of ADRD/Delirium. For Aim 2b, the study population will consist of adult (≥ 18) caregivers of patients identified in Aim 2a. These caregivers will be recruited to complete a phone survey for our secondary caregiver outcomes

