7.1 Subject Inclusion Criteria

Over the two years of the trial, we will examine data on approximately 15,000 patients ≥ 65 admitted to these 23* units for our primary and secondary outcomes (Aim 1). Given the pragmatic nature of this trial, our inclusion criteria are quite broad and consistent with the goal of pragmatic trials.

We will also survey caregivers of 600 patients with ADRD/Delirium to conduct a telephone administered survey for caregiver-centered outcomes (knowledge, confidence, communication satisfaction, decisional satisfaction, and decisional conflict) during the index hospitalization. Caregivers may or may not be designated as ADRD/Delirium legal surrogate decision maker for the patient (i.e., most patients with ADRD/Delirium do not have a legally designated representative.) Any adult identified in the EHR as the contact family member or friend will be eligible to partake in the caregiver survey. Half of surveys will be conducted during the control period; half during the intervention period. Caregivers will be either English- or Spanish-speaking adults, which are the languages in which our surveys are validated. For patients in the control group, surveys will be completed during the hospital stay or within 1 week of discharge. For patients in the intervention group, the survey will be completed AFTER the PCE intervention, and up to 1 week after discharge.

*14 units (7 per hospital) will be included in the stepped wedge trial, an additional 9 units (3 at BMC and 6 at NorthShore) will be used to recruit additional control participants only. These additional units were added due to low recruitment at the start of the study and the decreasing number of control units as the stepped wedge design progresses. The target enrollment of 600 caregivers is still accurate.

Adding delirium to the list of eligible diagnoses will also increase the potential number of eligible subjects. The surveys are applicable to the caregiver of any patient who is not capable of making their own health decisions; this includes patients who are experiencing any sort of memory or cognitive decline.

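### Section 12.2 labels the 90%-power sample size (440 per group, 2394 overall) as the 80% size, and its caregiver detectable effect of 0.53 does not follow from the stated inputs, which give about 0.38 SD

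*Combined protocol and SAP*

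**What the plan says.** All the figures are in section 12.2, Sample Size Determination, which opens with a general statement: "All sample size estimates here assume a minimum of 80% power and a two-sided alpha of 0.05".

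- **Primary outcome.** For 35% with ACP documentation under the intervention and 25% under usual care, "a sample size of 440 records per group in a chi-squared test for independent data will provide 80% power". With an ICC of 0.01 the design effect is given as 2.72, and the plan concludes that it needs "at least 2394 subjects overall (1197 per health system) to provide 80% power". It expects as many as 15,000 records.
- **Meaning of the design effect.** It is defined as "the factor by which the sample size found to provide sufficient statistical power for a meaningful intervention difference in outcome assuming independent data is multiplied". It is therefore a multiplier on sample size.
- **Caregiver outcomes (Aim 2b).** For about 600 caregivers and a design effect of 2.03, also at an ICC of 0.01, the minimum detectable effect "with 90% power and alpha=0.05 would be 0.53 after applying the design effect".
- **Caregiver allocation.** Section 5, Study Design, says that "600 caregivers of patients with ADRD/Delirium (300 control phase; 300 intervention phase) will be surveyed by telephone". Section 7.1 agrees: "Half of surveys will be conducted during the control period; half during the intervention period".

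**The concern.** Each calculation states enough inputs to be repeated, and neither gives the printed answer. For the primary outcome, 440 is well above the usual size for 25% versus 35% at 80% power, and the total of 2394 inherits the discrepancy. For caregivers, an effect as large as 0.53 SD is hard to reconcile with 300 per phase and a design effect near 2.

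A reader would take 2394 as the minimum for 80% power, and a 20% type II error at that size when it is really 10%. A reader of a null Aim 2b result would believe that effects between about 0.38 and 0.53 SD lay outside the study's 90%-power range. Section 12.3 commits to CONSORT reporting, so these figures are likely to be carried into the trial report.

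**Working it through.** **Primary outcome**

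Inputs from section 12.2: p1 = 0.25, p2 = 0.35, equal groups, chi-squared test for independent data, two-sided alpha 0.05, design effect 2.72.

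Formula: n per group = [z(0.975) x sqrt(2 x pbar x (1 - pbar)) + z(power) x sqrt(p1(1 - p1) + p2(1 - p2))]^2 / (p2 - p1)^2, with pbar = 0.30. The two square roots are sqrt(0.42) = 0.6481 and sqrt(0.1875 + 0.2275) = sqrt(0.415) = 0.6442.

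- The plan's 440 is reproduced at 90% power: (1.960 x 0.6481 + 1.2816 x 0.6442)^2 / 0.01 = 439.2, rounded up to 440.
- At 80% power: (1.960 x 0.6481 + 0.8416 x 0.6442)^2 / 0.01 = 328.5, rounded up to 329.
- Power at 440 per group is 0.9005. Simulation (400,000 trials, uncorrected chi-squared) gives 0.9006 at 440 and 0.8015 at 329.

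Other versions at 80% power do not reach 440: 349 with continuity correction, 326 with unpooled variance, 328 with the arcsine transformation, 259 one-sided. With continuity correction, power at 440 is 0.887.

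The total:

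- The plan's figure: 2 x 440 x 2.72 = 2393.6, or 2394. It follows from 440, so it is also a 90% size.
- At 80% power and the same design effect: 2 x 329 x 2.72 = 1789.8, about 1,790. That is 25% below 2394.

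**Caregiver outcomes**

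Inputs: 300 per phase (sections 5 and 7.1), design effect 2.03, 90% power and alpha 0.05 (section 12.2), two-sided testing (section 12.3). Assumption: 0.53 is in standard deviation units.

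Formula: detectable effect = [z(0.975) + z(power)] x sqrt(2 / n) x sqrt(design effect).

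- Independent data, 90% power: (1.960 + 1.2816) x sqrt(2 / 300) = 0.2647.
- With the design effect: 0.2647 x sqrt(2.03) = 0.377 (0.378 using the t distribution). Equivalently, the effective sample is 300 / 2.03 = 147.8 per phase.
- At 80% power: 0.326.
- Power for 0.53 with 147.8 effective per phase: 0.9953.
- Detecting 0.53 at 90% power needs only 74.8 effective per phase, which implies a design effect of 300 / 74.8 = 4.01, not 2.03.

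Other readings with 600 caregivers also miss 0.53: one-sided testing gives 0.340, and Bonferroni over the five outcomes gives 0.449.

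Two routes come close, and the documents show neither:

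- 300 caregivers in total (150 per group): 0.533.
- Multiplying by the design effect instead of its square root: 0.2647 x 2.03 = 0.537, or 0.26 x 2.03 = 0.528 if rounded first.

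**The case against.** The arithmetic is not in dispute. The case on the other side concerns how much it matters and what should replace the printed figures.

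- **The plan promises only a minimum of 80% power, and 440 per group exceeds it.** True, and the mislabelling does no harm to the design. But the specific sentences tie 80% power to 440 per group and give 2394 as the floor for that power. Those statements are incorrect.
- **Nothing depends on these figures.** Up to 15,000 records are expected, section 12.2 sets clinical significance by a 10-point absolute increase, and its conclusion about moderately sized effects holds at 0.38 or 0.53. This stands, and it limits the point to correcting the record.
- **1,790 is not a safe replacement.** By the plan's own account the design effect depends on the number of subjects per period, so a smaller total could change 2.72. Enrolment per period is not stated. This stands, and it favours relabelling over a new total.
- **0.53 may have an unstated basis.** Its units are not given, and 300 caregivers in total would produce it. A calculation per hospital is conceivable, since the primary size is also quoted per health system. But the text attaches 0.53 to about 600 caregivers, and the even split is documented. The possibility is a reason to ask for the derivation.
- **0.38 relies on 2.03 still applying.** That design effect is stated for seven clusters, while section 7.1 adds nine control-only units for recruitment. This is a fair caution: 0.38 is what the stated inputs imply, and 2.03 itself cannot be verified from the documents.

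**Conclusion.** The concern holds for both figures.

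- **Primary outcome:** 440 per group and 2394 overall carry 90% power, not 80%. This needs no assumption beyond the plan's stated inputs, with 2.72 taken as given for the total.
- **Caregivers:** the stated inputs give a detectable effect of about 0.38 SD at 90% power, so 0.53 is overstated by roughly 40% (0.53 / 0.377 = 1.41). This assumes SD units, the documented 300/300 split and the stated design effect of 2.03. How 0.53 arose cannot be settled from the documents.

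Both errors understate what the design can do. They are errors in the stated figures and do not threaten the adequacy of the trial.

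**What to change.** Two wording changes in section 12.2:

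1. State that 440 per group, and 2394 overall (1197 per health system), provide 90% power. The alternative is to quote 329 per group and about 1,790 overall for 80% power, but that total is valid only if the design effect stays at 2.72. Relabelling is the safer choice.
2. Replace 0.53 with about 0.38 SD at 90% power for 600 caregivers, 300 per phase, design effect 2.03. If 0.53 is to stay, show its derivation, including units, sample size and allocation. In either case, confirm that 2.03 still applies now that the nine control-only units contribute caregivers.

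The cost is an edit to the protocol and SAP text. Enrolment and analysis do not change.

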12.3 Statistical Methods

Statistical Analysis: For the primary analyses of the primary and secondary outcomes, there will be no crossover of data for subjects from usual care to the intervention during the study; that is, subjects will only contribute data once during the course of the study, from their index hospitalization. Similarly, patients who move units during the course of their index hospitalization will be assigned to contribute intervention time data if they spend at least eight daytime weekday hours after being identified as meeting the inclusion criterion on a clinical unit where the intervention is being conducted. Accordingly, data being contributed by patients at each site during the pre-intervention period and data being contributed by patients after the initiation of the intervention will be kept separate for initial analyses. However, because we expect some patients to have multiple hospitalizations during different steps or to different units (i.e., crossover design), we will perform secondary analyses on all outcomes including data from the index hospitalization. This will include stratified sensitivity analyses of patients who contribute data (a) only to control period; (b) only to intervention period; or, (c) to both control and intervention periods.

Given the randomized nature of the stepped wedge design, we will report our results according to CONSORT guidelines. For the aims of the study that require patient/caregiver enrollment (Aim 2), we will record the number of people approached, screened, ineligible, and refusing participation. We will record subject attrition and note all adverse events. We will employ the intent-to-treat principle in our comparative analyses between the intervention and usual care groups. All hypothesis tests will employ a two-sided alpha level of 0.05. Given that the primary aim will be addressed by the analysis of data obtained from available patient records for the study period, we will examine the distributions of relevant variables focusing on the data relating to the documentation of ACP, the outcome of this aim. For the secondary aims of the study that will require enrollment of a caregiver sample for interview (Aim 2), we will examine the

distributions of the uncertainty and knowledge scale scores, the outcomes of interest between intervention and usual care subjects, as well as the distributional characteristics of all other salient study variables. We will generate descriptive statistics (means, standard deviations, quantiles for continuous variables; counts and percentages for categorical variables) and schematic plots (box-and-whisker, quantile-quantile plots). Given the nature of the cluster randomization that we will employ, we will utilize statistical analytic methods that take the correlated nature of the data into account as well as the influence of time to account for secular trends. In this study, we will examine both the health system and hospital unit as clustering variables, with the hospital unit as the primary clustering variable. We will compare the intervention and usual care groups on salient variables in order to assess balance in the distributions of these variables. Variables found to differ between the study groups will be further evaluated to assess their confounding effects of intervention vs. usual care differences on outcomes in multivariable analyses for correlated (clustered) data.

Aim 1. To test the combined effects of a COVID-19 ACP Educator-led, video-assisted palliative care intervention on rates of: ACP documentation; Medical orders for resuscitation preferences in the EHR; Palliative Care Consults; and, Hospice use. ***Hypothesis: A higher proportion of patients in the intervention phase (vs. control) will: complete ACP documentation (primary trial outcome), have documented orders for resuscitation preferences, have palliative care consults, and enroll in hospice.***

Primary outcome: ACP documentation. In order to formally estimate and test differences in the proportion of patients with documentation of ACP between the intervention and usual care groups, we will employ logistic regression models for correlated binary outcome data. These models will either involve the use of robust variance methods to account for the clustering of these data by hospital site and/or health system via generalized estimating equations (GEE) or the inclusion of a random effects terms (in which case, the results will be interpreted as cluster-specific). Other potential modifiers of the effect of intervention, confounding variables, or covariates can be added to this model as fixed effects. Although we do not expect effect modification in the study data, we will examine the potential for such effects (interaction) through the use of stratified analyses and the inclusion of interaction terms with study group in our statistical models. Candidate effect modifiers will be specified a priori and will include age, gender, race/ethnicity, religion, and language. We will also examine and incorporate secular trend effects, i.e., the effect of time over the course of the study. Statistically significant interactions with the intervention will be retained and the nature of heterogeneous intervention effects will be estimated using the interaction model.

Based on our prior work in which we exhibited the fact that African-American and Hispanic patients are at particularly high risk for lower level of knowledge related to ACP, not discussing ACP with family, not having a health care proxy, and not having ACP documentation, we anticipate that this intervention may be particularly beneficial for African-American and Hispanic patients.(115, 131, 132) Accordingly, we will evaluate heterogeneous treatment effects by race and ethnicity and anticipate having adequate diversity in our study population to make such assessments. All data regarding Aim 1 will come from the EHR. Our institutions maintain excellent self-report information regarding race and ethnicity.

We will conduct analyses related to potential effect modification as a step in our model validation process and to identify relationships that can be examined more fully in future research. Should interactions not be found to be statistically significant, we will fit a main effects-only model and use it to formally evaluate confounding by applying a change-in-estimates approach, with a 10% change in estimates being an initial screening criterion. **Secondary outcomes:** Similar procedures will be undertaken to assess intervention effects for the other EHR derived outcomes (documented orders for resuscitation preferences, palliative care consults, hospice enrollment, and documented health care proxies).

For our primary analysis, we will consider our primary outcome (ACP documentation) and our secondary outcomes (resuscitation preferences, palliative care, hospice use, and health care proxies) only for the patient's index hospitalization. However, because we expect some patients to have multiple rehospitalizations during the same step and may also include intervention time (i.e., crossover design), we will perform secondary analyses on all of our primary and secondary outcomes for each patient reviewing all EHR records from the index hospitalization of the patient until their death (or through study period). We will also perform stratified sensitivity analyses of patients who contribute only to control period vs. patients who contribute only to intervention period vs. those that contribute to both control and intervention periods.

We will conduct the above analyses on all Aim 1 and Aim 2a patients for the study primary and secondary outcomes.

Aim 2b. To characterize detailed caregiver-centered outcomes, including knowledge, confidence in future care, communication and decisional satisfaction, and decisional certainty in a group of caregivers of patients with ADRD/Delirium admitted to the hospital. **Hypothesis:** *Caregivers in the intervention phase (vs. control) will have higher knowledge, confidence in future care, improved communication and decisional satisfaction, and less decisional conflict.* For Aim 2b, we will compare survey responses from intervention and control periods to take into account clustering within clinical unit and hospital. We will include calendar time and any imbalance from caregiver characteristics in the model to adjust for the potential confounding factors. We will account for clustering using methods as described above but will employ linear models for correlated data fitted via GEE or in mixed models.

Missing data: We will impute data when missing using multiple imputation techniques. This approach is one of the statistically principled methods noted in a recent *NEJM* editorial on the need for such approaches in the analysis of data from RCTs with missing values.(141) This approach assumes that data are missing either completely at random (MCAR) or at random (MAR) as a function of non-missing data on available variables in the dataset. We will implement this process using PROC MI in SAS. We will generate 20 imputed datasets and will conduct our intent-to-treat analyses per our analysis plan, saving results across datasets so they can be combined using PROC MIANALYZE in SAS. We will also consider the possibility that data are missing in a non-ignorable fashion. For example, should more or less symptomatic subjects be lost to follow-up as a result of treatment – and thus produce results that are biased in a manner not addressable by the above methods that assume MCAR or MAR data – we will randomly

impute data in sensitivity analyses under various alternative scenarios employing multiple imputation with the combination of analytic results noted above.

Reporting dropout and missing data. Whenever a participant in the caregiver interview sample drops out of the study, we will document the specific reason for dropout, who decided that the participant would drop out, and whether the dropout involved intervention participation, data collection, or both. If a participant withdraws from the intervention only, we will continue to collect data on all outcome measures. All participants included will be accounted for in a CONSORT diagram.

13 Ethics/Protection of Human Subjects

This study is to be conducted according to applicable U.S. federal regulations and institutional policies (which are based in federal regulations, guidance, and ICH Good Clinical Practice guidelines).

This protocol and any amendments will be submitted to the BMC IRB, for formal approval of the study conduct. The decision of the IRB concerning the conduct of the study will be made in writing to the investigator. A copy of the initial IRB approval letter will be provided to the sponsor before commencement of this study.

All subjects enrolled for Aim 2 (caregiver survey) will provide verbal informed consent by phone prior to answering any survey questions. Subjects will be provided with sufficient information and time to make an informed decision about their participation in this study. These subjects will be offered to have a copy of the consent form mailed to them (Email or US Mail) to keep for their records. The consent form will be submitted with the protocol for review and approval by the IRB. The consent of a subject, using the IRB-approved consent form, must be obtained before that subject is submitted to any study procedure. Consent will be documented as required by the IRB.

Literature References

